# **PROTOCOL SUMMARY**

Ctudy Title Detroppeding Deat Market Clinical Follows I in Ctudy of				
Study Title	Retrospective Post-Market Clinical Follow-Up Study of Vascular Graft in Peripheral			
	Artery Disease, Aortic Aneurysms and Dialysis Access.			
Protocol Number	VGP 21-01			
Sponsor	W. L. Gore & Associates, Inc.			
	Medical Products Division			
	[contact]			
Local	Gore Authorized Representative			
Representative	W. L. Gore & Associates B.V.			
Coordination PI				
Obitionation	The primary objective is to confirm the clinical performance and safety of			
Objective	Vascular Graft throughout the device functional lifetime for each indication for use.			
Study Design	Multicenter, single-arm retrospective study			
Tracy 2 cong.:	manassiner, emg.e amm reaceposite statuy			
Study Devices				
Out to at Douglation	Patients that have had treatment with			
Subject Population	Vascular Grafts for peripheral artery disease (PAD), aortic aneurysms, or dialysis access.			
	Patient is willing and able to provide written informed consent or			
General Inclusion	consent is waived.			
Criteria	2. Patient was at least 18 years of age at the time of implant.			
	Patient was not available for follow up (on-site or remotely) at the			
	clinical site, with the exception of death (e.g., patient lost to follow-up			
	immediately after treatment, patient who lives far away from the			
	treatment site and not available to share follow-up data performed			
	locally).  2. At the time of treatment, patient had known coagulation disorders,			
General Exclusion	including hypercoagulability, that were not amenable to treatment.			
Criteria	Patient was pregnant at the time of treatment.			
	4. Patient had known or suspected systemic infection or infection at the			
	site of graft implantation at the time of implant.  5. Patient had a separate major interventional or surgical vascular			
	procedure within 30 days prior to treatment. CVC catheter placement			
	would be permitted.			
	6. Patient is already enrolled in this registry under a different cohort.			
Davinhanal Astan	Primary Safety Outcome: Device-related seroma or			
Peripheral Artery Disease Cohort	Clinical   infection at 5 years     Outcomes   Primary Performance Outcome: Secondary patency			
5.000.00	(revascularization) through 5 years			
	1 1 1 7 7			

	Follow-Up Sample Size	Secondary Outcomes:  Limb Salvage through 1 year  Amputation Free survival through 1 year  Device-related Adverse Events through 1 year  Device-related infection requiring reoperation through 5 years  Primary Patency through 1 year  Years  Patients with any
	PAD Cohort Inclusion Criteria	Patient was treated for peripheral arterial disease or peripheral arterial aneurysm requiring bypass with  Vascular Graft at least 5 years before site initiation.
	PAD Cohort Exclusion Criteria	At the time of treatment, the patient must not have met any of the following criteria:  1. Patient had percutaneous transluminal angioplasty (PTA) or stenting of the target artery at the anticipated site of the proximal or distal anastomosis within 30 days prior to the index procedure. Use of PTA or stenting during the index procedure is permitted.  2. Patient had a stroke or myocardial infarction (MI) within 6 weeks prior to the index procedure.  3. Patient has previous instance of Heparin-induced Thrombocytopenia type 2 or has known hypersensitivity to heparin.  4. Patient required composite bypass for index procedure (graft + significant length of autologous vessel). Autologous "cuffs" or patches are allowed.
	Clinical Outcomes	Primary Safety Outcome: Survival at 5 years Primary Performance Outcome: Primary patency at 5 years
	Follow-Up	5 Years
	Sample Size	65 Patients with
Aortic Aneurysm Cohort	Aortic Aneurysm Cohort Inclusion Criteria	Underwent simultaneous or staged aortic aneurysm repair (open surgical AAA or TAAA) involving a  Vascular Graft at least 5 years before site initiation. Research device could have been used to replace or bypass either a diseased visceral branch or the aorta itself.
	Aortic Aneurysm Cohort	Patients required emergency surgery at the time of implant due to aneurysm rupture.

	Exclusion Criteria			
	Clinical Outcomes	Primary Safety Outcome: Device-related infection through 2 years  Primary Performance Outcome: Useable access circuit (reported as secondary patency) through 2 years  Secondary Outcomes:  Primary patency through 1 year  Device-related adverse events through 1 year		
	Follow-Up	2 years		
	Sample Size	72 patients implanted with any 72 Patients implanted with any		
Dialysis Access Cohort	Dialysis Access Cohort Inclusion Criteria	Patient required the creation of a vascular access graft for hemodialysis secondary to a diagnosis of End-Stage Renal Disease using a  Vascular Graft,  Vascular Graft at least 2 years before site initiation with the intent to cannulate the registry device.		
	Dialysis Access Cohort Exclusion Criteria	At the time of treatment, the patient must not have met the following criteria:  1. The patient had a previous documented (via imaging technique) and unsuccessfully treated ipsilateral central venous stenosis.  2. The patient was taking maintenance immunosuppressant medication at the time of implant such as rapamycin, mycophenolate or mycophenolic acid, prednisone (> 10 mg), cyclosporine, tacrolimus, or cyclophosphamide.  3. The patient has had a previous instance of Heparin-Induced Thrombocytopenia type 2 (HIT-2) or has known sensitivity to heparin.		
Number of Sites	Up to 9 sites in E			
Schedule of Events	Pre-enrollment: P treated with Vascular Grafts a Procedure: Patier retrospectively co	Grafts and deemed suitable for inclusion.  E: Patient procedural and adverse event information will be ively collected.  E: Patient records will be collected for 2-5 years post-procedure		
Additional Information	Contract Researc	h Organization:		

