### 4. Study Population

# 4.1. Description of Population

The study population will consist of three cohorts. Patients that have had treatment with Vascular Graft for PAD, aortic aneurysms, or dialysis access are eligible for consideration for enrollment in the registry.

Cohort	Treatment period	FU period after index procedure (years)	Number patients	Cap per site** (patient)
PAD	at least 5 years before site	5*		18 (25%) 36 (50%)
	initiation			18 (25%) 36 (50%)
Aortic Aneurysms	at least 5 years before site initiation	5*		16 (25%) 33 (50%)
Dialysis Access	at least 2 years before site initiation	2*		18 (25%) 36 (50%)
, 100000				18 (25%) 36 (50%)

\* Subject who died before the end of FU period will be not excluded from the registry.

Study staff will review patients' medical records to identify eligible patients for this retrospective data collection. The registry has been designed with standard eligibility criteria to enroll subjects for which the registry device has been intended to treat. Two sets of inclusion and exclusion criteria have been identified: general and cohort-specific criteria. Only patients who meet all of the inclusion criteria and none of the exclusion criteria (general and cohort-specific) will be included in the registry. A subject cannot be included in more than one cohort.

No vulnerable populations are included in this registry.

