### 4.2.4. Dialysis Access Cohort Inclusion Criteria

### 4.3. Exclusion Criteria

### 4.3.1. General Exclusion Criteria

- 1. Patient was not available for follow up (on-site or remotely) at the clinical site, with the exception of death (e.g., patient lost to follow-up immediately after treatment, patients who live far away from the clinical site and are not available to share follow-up data performed locally).
- 2. At the time of treatment, patient had known coagulation disorders, including hypercoagulability, that were not amenable to treatment.
- 3. Patient was pregnant at the time of treatment.
- 4. Patient had known or suspected systemic infection or infection at the site of graft implantation at the time of implant.
- 5. Patient had a separate major interventional or surgical vascular procedure within 30 days prior to treatment. CVC catheter placement would be permitted.
- 6. Patient is already enrolled in this registry under a different cohort.

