### 5.12. Subject Lost to Follow Up

No subject lost to follow up are expected in this registry. According to General Exclusion criterion #1, subjects with no follow-up after treatment should not be included in the registry. All subjects that complete at least one follow-up after treatment will be enrolled.

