### 9.1.3. Adverse Event Reporting and Coding

health is not considered serious.

Considering the retrospective nature of the registry only AEs already documented in the subject's medial record will be reported on the appropriate CRF.

No follow-up related to the open adverse event in order to obtain new information is required for this registry.

The investigator at each site is ultimately responsible for reporting AEs to the sponsor.

The following information on each reported AE will be collected:

- Adverse event name
- Adverse event onset date
- Relationship
- Classification serious or non-serious
- Outcome
- Resolution date

Adverse events will be coded using the Medical Dictionary for Regulatory Activities (MedDRA).

Adverse event submission guidelines:

- Adverse event reporting begins once the patient is enrolled in the registry (ICF signed or waived). All adverse events should be reported from index procedure through registry completion / discontinuation.
- Provide a diagnosis if possible. If unable to provide a diagnosis, report the symptoms as separate events. Adverse events should be reported using the full name without abbreviations or narratives.
- Adverse events ongoing at registry completion / discontinuation should be left as "ongoing" on the AE case report form.
- Medical condition and adverse event observed at the time of treatment will be part in the medical history of the patients. Adverse events will be reported in the EDC only if they become serious or increase in intensity, or if a worsening of a baseline condition.

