# **Registry-Specific Appendices**

# Appendix A: Eligibility Criteria with Justification / Rationale

# **General Inclusion & Exclusion Criteria**

Item Number	Text of Criterion	Rationale
Inclusion 1	Patient is willing and able to provide written informed consent or consent is waived.	Required element of ISO 14155 and other regulatory guidelines
Inclusion 2	Patient was at least 18 years of age, at the time of implant.	Patients younger than 18 would be considered a vulnerable population.
Exclusion 1	Patient was not available for follow up (on-site or remotely) at the clinical site, with the exception of death (e.g., patient lost to follow-up immediately after treatment, patient who lives far away from the treatment site and not available to share FU data performed locally).	Ensures a reasonable expectation of follow up.
Exclusion 2	At the time of treatment, patient had known coagulation disorders, including hypercoagulability, that were not amenable to treatment,	As device patency is under examination, coagulation disorders could confound data. It is expected that medications will change over the follow up period, patients have poor compliance & meds may not be documented well retrospectively.
Exclusion 3	Patient was pregnant at the time of treatment.	Potential device effects on a pregnant woman or fetus have not been nor are desired to be evaluated. Study Subjects are expected to receive radiation as part of the index procedure and recommended follow-up procedures.
Exclusion 4	Patient had known or suspected systemic infection or infection at the site of graft implantation at the time of implant.	Infections could lead to adverse events and confound the interpretation of study results.
Exclusion 5	Patient had a separate major interventional or surgical vascular procedure within 30 days prior to treatment. CVC catheter placement would be permitted.	Additional procedures could confound endpoints. While scheduled post treatment procedures were initially included, team felt this would be hard to capture. This will be captured in the CRFs if available.
Exclusion 6	Patient is already enrolled in this registry under a different cohort	Patients enrolled in multiple arms could confound the study results.

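### General Exclusion 1 selects on follow-up after treatment and exempts only death, so charted non-fatal early failures can be dropped and results are unbiased only if leaving is unrelated to index-stay outcome

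*Protocol*

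**What the plan says.** The ground for exclusion in Protocol 4.3.1 is not being "available for follow up (on-site or remotely) at the clinical site, with the exception of death (e.g., patient lost to follow-up immediately after treatment". The Summary states the same rule ("clinical site, with the exception of death (e.g., patient lost to follow-up"), as does Appendix A, which gives as its reason "Ensures a reasonable expectation of follow up". Section 5.12, repeated in SAP 4.0, applies it: "subjects with no follow-up after treatment should not be included in the registry". The same section then sets the entry threshold: "All subjects that complete at least one follow-up after treatment will be enrolled". Section 4.1 keeps deaths: "Subject who died before the end of FU period will be not excluded from the registry".

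The endpoints nevertheless start at implantation. Section 5.8.2 collects procedure, discharge, reintervention and adverse event data, and under 9.1.3 "All adverse events should be reported from index procedure through registry completion / discontinuation".

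For analysis, SAP 5.0 specifies two-sided exact binomial 95% intervals and leaves out subjects whose outcome is missing. SAP 8.1 lists Kaplan-Meier estimates for all the primary and secondary endpoints.

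**The concern.** General Exclusions 2 to 5 concern the patient's state at or before implant. Exclusion 1 is settled afterwards, when early outcomes are already known. An unrestored occlusion, an abandoned access, a device-related infection or an above-ankle amputation in the index stay decides an endpoint. If that patient survives and has no later contact with the site, the criterion removes a known event.

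Nothing else in the plan brings the patient back:

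- The consent waiver (3.2.1, 5.2) deals with consent, not eligibility.
- The calls to relatives or the general practitioner (5.10) concern subjects already enrolled.
- Only enrolled patients enter the database, and non-enrolment is logged with a single principal reason (5.4).
- The pre-screening log stays at the site (5.3).

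The sponsor's analysis therefore cannot show how many known events were removed.

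At stake are PAD seroma or infection, patency, limb salvage and device-related adverse events, and dialysis infection, patency and device-related adverse events. Aortic primary patency is exposed in the same way. Amputation-free survival is treated unevenly: early deaths are always kept, early amputations followed by loss are not.

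**Working it through.** **Scale for comparison.** The plan's precision figures reproduce. With 72 patients at 55%, the exact 95% half-width is 11.97%. With 65 patients it is 11.88% at 32% and 11.97% at 33%.

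**Inputs.** True patency of 55% is the planning rate in Protocol 10.2. The documents give no rate of index-stay failure and no rate of leaving. Assumed here: 10% index-stay failure that is not restored, 5% leaving among non-failures, and a leaving rate L among failures that is varied. Leaving among non-failures is taken as unrelated to their later patency.

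**Current rule.** Take 1,000 eligible implants:

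- Index-stay failures: 100. Non-failures: 900, of whom 550 are patent at the end.
- Non-failures kept: 900 × 0.95 = 855, of whom 550 × 0.95 = 522.5 are patent.
- Failures kept: 100 × (1 − L).
- Reported patency = 522.5 / (855 + 100 × (1 − L)).

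| L, leaving among failures | Calculation | Reported patency |
|---|---|---|
| 2% | 522.5/953 | 54.8% |
| 5% (same as non-failures) | 522.5/950 | 55.0% |
| 10% | 522.5/945 | 55.3% |
| 20% | 522.5/935 | 55.9% |

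With equal leaving, the index-stay failure proportion is also unchanged: 95/950 = 10%, the same as 100/1,000. At L = 20% it reads 80/935 = 8.6%.

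**Infection, a bounding case.** Assume a true rate of 5%, all of it in the index stay, and 5% leaving among the uninfected. Of 1,000 implants, 950 × 0.95 = 902.5 uninfected patients remain, and the reported rate is 50(1 − L) / (902.5 + 50(1 − L)).

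- L = 10%: 45/947.5 = 4.7%.
- L = 20%: 40/942.5 = 4.2%, about 15% below the true rate in relative terms.
- L = 2%: 49/951.5 = 5.1%, about 3% above it.

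If only some infections arise in the index stay, the shift is smaller. The 20% case moves patency by 0.9/55, or 1.6% in relative terms.

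**Keeping these patients.** With Kaplan-Meier, all 100 index-stay failures count and the 45 event-free leavers are censored at discharge. The estimate is 0.90 × 522.5/855 = 55.0% whatever L is. With the complete-case rule in SAP 5.0, all 100 failures count but the 45 event-free leavers drop out as missing: 522.5/955 = 54.7%. The estimator therefore has to change along with the criterion.

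**The case against.** The strongest reply is that the criterion removes event-free leavers as well as failures, so it has no built-in direction. That stands, as the 55.0% row shows. A reader might infer that the rule can only flatter the device, because an event-free leaver adds nothing to a Kaplan-Meier curve after discharge, and might write reported patency as 0.55/(1 − E), with E the share of implants that failed and left. The documents do not support this. Event-free leavers still belong in the denominator for the index stay, and the formula treats everyone excluded as a failure. With equal leaving, E is 5/1,000 = 0.5% and the formula gives 55.3%, when the true and reported values are both 55.0%.

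Second, follow-up is not defined. Section 5.10 lists adverse events and repeat interventions among follow-up data, so a site might treat an in-hospital record as follow-up and enrol the patient. Patients reachable remotely also stay in. This narrows the affected group. But the criterion's own example, a patient lost immediately after treatment, points the other way, and leaving the choice to sites is itself a weakness.

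Third, the study is descriptive, the reason for the criterion is disclosed, enrolment is consecutive, and monitors check the logs on site (5.4). That check shows patients were taken in sequence; it does not return the excluded events to the analysis. The patency shifts above are under 1 point against a half-width of about 12, which limits the importance of the point but does not remove it.

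**Conclusion.** The point holds as a selection problem of unknown direction. The plan's estimates are unbiased only if leaving the site is unrelated to what happened in the index stay, and the documents offer no support for that. If failures leave more often, patency and limb salvage read too high, and infection and device-related adverse event rates too low. If failures leave less often, the reverse holds.

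Under the stated assumptions patency is reported between 54.8% and 55.9% for a true 55%. The effect is probably small there and could be larger in relative terms for infection, a primary safety outcome in the PAD and dialysis cohorts. An occlusion that was reopened counts against primary patency only; secondary patency is affected only by grafts not restored or access abandoned. The index-stay failure rate, the leaving rates and the infection rate are all assumptions.

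**What to change.** In the Summary, 4.3.1, 5.12, Appendix A and SAP 4.0, limit Exclusion 1 to patients with no post-procedure record at all, including the index admission and discharge record. Count index-stay events as events, and censor event-free patients at their last documented contact, which is discharge if there is none later.

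Make the Kaplan-Meier estimate with its 95% confidence interval, already listed in SAP 8.1, the reported estimate for these endpoints, and align Protocol 10.1 and SAP 2.5 and 5.0 with it. Changing the criterion while keeping the exact binomial complete-case analysis would bias patency downward. Report the number of patients excluded under criterion 1.

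The cost is a few short charts to abstract with the usual consent or waiver handling (5.2 already allows a waiver for unreachable patients, subject to national and local law), some subjects with very short follow-up, and slightly less precision at the fixed sample size.

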### **LIST OF ABBREVIATIONS**

AAA Abdominal Aortic Aneurysms

AE Adverse Event

ACC/AHA American College of Cardiology/American Heart Association

ADE Adverse Device Effect
ALI Acute Limb Ischemia
AVF Arteriovenous Fistulae
AVG Arteriovenous Grafts

CDMS Clinical Data Management System

CE Conformité Européenne
CIP Clinical Investigation Plan
CKD Chronic Kidney Disease
CLI Critical Limb Ischemia

CLTI Chronic Limb-Threatening Ischemia

CRF Case Report Form

CRO Contract Research Organization

CVC Central Venous Catheters

EC Ethics Committee

eCRF Electronic Case Report Form

ePTFE Expanded Polytetrafluoroethylene

ESRD End Stage Renal Disease

ESVS European Society of Vascular Surgery

EU European Union

EVAR Endovascular Aneurysm Repair

FDA Food and Drug Administration (United States)

FP Femoropopliteal Occlusions

FEP Fluorinated Ethylene Propylene

Fr French (sizing)

GCP Good Clinical Practice
GFR Glomerular Filtration Rate

Gore W. L. Gore & Associates, Inc.

HE Health Economics

IB Investigators Brochure

MD133246 Protocol Template Page v

ICF Informed Consent Form

ICH International Conference on Harmonization

IDE Investigational Device Exemption

IFU Instructions for Use

PAD Peripheral Artery Disease
PHI Protected Health Information

PI Principal Investigator

PTA Percutaneous Transluminal Angioplasty

RRT Renal Replacement Therapy

SAE Serious Adverse Event

SFA Superficial Femoral Artery

SAA Splenic Artery Aneurysms

SVS Society of Vascular Surgery

TAAA Acute Thoracoabdominal Aortic Aneurysm

US United States

USADE Unanticipated Serious Adverse Device Effect

### **DEFINITIONS**

**Adverse Event:** Untoward medical occurrence, unintended disease or injury, or untoward clinical signs (including an abnormal laboratory finding) in subjects, users, or other persons, whether or not related to the investigational medical device and whether anticipated or unanticipated.

**Adverse Device Effect:** Adverse event related to the use of an investigational medical device

**Clinical Investigation Plan:** Documents that describes the rationale, objectives, design and pre-specified analysis, methodology, organization, monitoring, conduct and record-keeping of clinical investigation. These documents may include the protocol, monitoring plans, and statistical analysis plans.

**Device Deficiency:** Inadequacy of a medical device with respect to its identity, quality, durability, reliability, usability, safety or performance.

**Enrollment:** A patient is considered enrolled into the registry once informed consent has been signed and dated or consent if waived.

**Registry Device:** The medical device being assessed for safety or performance in this registry. May also be referred to as registry device. This includes medical devices already on the market that are being evaluated for new intended uses, new populations, new materials, or design changes.

**Serious Adverse Event:** Any adverse event that led to any of the following: death; serious deterioration in the health of the subject, users, or other persons as defined by one or more of the following: life-threatening illness or injury, permanent impairment of a body structure or a body function, hospitalization or prolonged of patient hospitalization, medical or surgical intervention to prevent life-threatening illness or injury or permanent impairment to a body structure or a body function, chronic disease; or fetal distress, fetal death, or a congenital physical or mental impairment or birth defect. Defined in more detail in section 9.

**Serious Adverse Device Effect:** An adverse device effect that has resulted in any of the consequences characteristic of a serious adverse event.

**Unanticipated Serious Adverse Device Effect:** Serious adverse device effect which by its nature, incidence, severity, or outcome has not been identified in the current risk assessment.

